4.6.3.11 Clinical Global Impression of Change (CGI-C)

CGI-C is an observer-rated 7-point scale that measures patient total improvement relative to the investigator's past experience with other patients with the same diagnosis, with or without collateral information. The 7 improvement categories are: very much improved; much improved; minimally improved; no change; minimally worse; much worse; very much worse. The CGI-C will be evaluated at early termination and the following visits: Weeks 12, 24, 36 and 52 for the 52-week PRN (2-8) and (9-14) dosing groups; Week 12 for the 12-week EOD+PRN and PRN (2-8) dosing groups.

The number and percentage of subjects in each category will be tabulated at each scheduled visit and the last post-baseline visit by enrollment group and overall. Percentages for categories will be based on subjects with non-missing data at each visit, along with two-sided Agresti-Coull 95% CIs for each percentage. Refer to the BHV3000 Core SAP for additional combined categories.

4.7 Pharmacokinetic Evaluations

No pharmacokinetic data were collected in this study.

4.8 Safety Analysis

Safety analyses will be conducted on treated subjects by enrollment group and overall, unless otherwise noted. Safety outcome measures include: AEs, laboratory assessments including liver toxicity, vital signs, physical measurements, electrocardiograms (ECGs), and S-STS.

Select safety parameters will be summarized as continuous parameters at baseline and each scheduled visit over time during the on-treatment and follow-up safety analysis periods. Post-

baseline measurements will be first slotted into analysis visit windows in the post-enrollment and follow-up analysis periods (see Section 5.4). Post-baseline measurements will then be slotted into safety analysis periods (on-treatment and follow-up). If a subject has multiple values in an analysis visit window during a safety analysis period, then the non-missing value closest to the target date for the visit will be used; in the case of a tie, the latest value collected (from the central laboratory, if applicable) will be used. In these tables, the latest non-missing value collected (from the central laboratory, if applicable) among those at analysis visits Weeks 2 to 56 that fall in the follow-up safety analysis period will be summarized under the “Follow-up EOT” visit. See Sections 4.5, 5.4 and 5.5 for definitions of baseline, analysis periods, and analysis visit windows, respectively.

By-subject listings of safety data are described in subsections. In addition, a by-subject listing of procedures will be provided for screened subjects.

A by-subject listing of safety narrative subject identifiers will be provided for screened subjects with select events, as described in the BHV3000 Core SAP. The listing will flag subjects with select events.

4.8.1 *Extent of Exposure*

Study medication is rimegepant 75 mg tablet. This is dispensed in bottles containing 30 tablets of 75 mg rimegepant at the baseline visit and at study visits as needed; subjects should finish a bottle of study medication (containing 30 tablets of drug) prior to starting a new bottle.

Subjects are instructed to provide study drug taken status (yes, no) and number of tablets in their eDiaries every day after they are determined to be eligible to take study drug. If a subject did not report any study drug data in the eDiary on a given day, then it is assumed that the subject did not take study drug that day. Study drug records will come from the treatment epoch.

Drug accountability is provided by the site on the Drug Accountability CRF.

A by-subject listing will present eDiary exposure (i.e., number of tablets taken) and drug accountability for treated subjects.

Another by-subject listing will present eDiary exposure (i.e., total number of tablets taken) in 4-week intervals during the LTT for treated subjects. This will also display cumulative rimegepant exposure from both sources (i.e., eDiary and drug accountability), and flag subjects with ≥ 10 cumulative tablet difference between the 2 sources.

Another by-subject listing will present batch numbers for treated subjects.

eDiary Exposure

eDiary exposure will be summarized descriptively for treated subjects by enrollment group and overall, and will include the following parameters:

- Time in the OP (weeks), defined as (OP end date – OP start date + 1)/7
- Time from enrollment to last contact (weeks), defined as (last contact date – IWRS enrollment date + 1)/7
- Time in the LTT period (weeks), derived as (LT_T end date – LT_T start date + 1)/7
- Time on rimegepant (weeks), derived as (study drug end dose date – study drug first dose date + 1)/7.*
- Cumulative rimegepant exposure (tablets), derived by summing number of tablets across records with complete dates for subjects who reported taking study medication during the treatment epoch in the eDiary.*
- Average rimegepant exposure (tablets per 4 weeks), derived as 4*cumulative rimegepant exposure/time in the LTT period.*
- Number and percentage of subjects in the average rimegepant exposure (tablets per 4 weeks) categories defined in Section 4.2.6, and also in the following categories:
 - ≥ 12.6 ($\geq 90\%$ compliant with EOD dosing)
 - ≥ 11.2 ($\geq 80\%$ compliant with EOD dosing)
- Number and percentage of subjects who took more than 1 tablet per day on any day. This could be from the same bottle or different bottles due to an unscheduled visit.
- Exposure over time, as defined by the number and percentage of subjects who took
 - ≥ 8 tablets per 4 weeks for 4, 8, 12, 16, 20, ≥ 24 , ≥ 12 , and ≥ 4 weeks. These categories correspond respectively to 1, 2, 3, 4, 5, ≥ 6 , and ≥ 3 4-week intervals that are not necessarily consecutive (see below)
 - ≥ 12 tablets per 4 weeks for 4, 8, 12, 16, 20, ≥ 24 , ≥ 12 , and ≥ 4 weeks
 - ≥ 13 tablets per 4 weeks for 4, 8, 12, 16, 20, ≥ 24 , ≥ 12 , and ≥ 4 weeks
 - ≥ 14 tablets per 4 weeks for 4, 8, 12, 16, 20, ≥ 24 , ≥ 12 , and ≥ 4 weeks (the “ ≥ 12 weeks” category will support the subgroup “treated subjects who took ≥ 14 tablets per 4 weeks for ≥ 12 weeks” specified in Section 4.2.6)
 - ≥ 20 tablets per 4 weeks for 4, 8, 12, 16, 20, ≥ 24 , ≥ 12 , and ≥ 4 weeks
 - ≥ 25 tablets per 4 weeks for 4, 8, 12, 16, 20, ≥ 24 , ≥ 12 , and ≥ 4 weeks
- Total rimegepant exposure (tablets) summed across all subjects, derived by summing cumulative exposure across all subjects
- Total rimegepant exposure (patient-years), derived by summing (study drug end dose date – study drug first dose date + 1)/365.25 across all subjects.

This summary will also display quintiles (e.g., P20, P40, P60, P80, where “PX” denotes Xth percentile) for asterisked (“*”) continuous parameters to support the derivation of rimegepant exposure subgroups (see below). See Section 5.3 for derived dates.

eDiary exposure over time will assess the number of 4-week (28-day) intervals in which a subject exceeded select tablet counts in the LTT analysis period (see Section 5.4), where the number of 4-week intervals are not necessarily consecutive. For example, suppose a subject takes 20 tablets through 4 weeks (interval 1; LTT study days 1 to 28), 10 tablets after 4 weeks to 8 weeks (interval 2; LTT study days 29 to 56), 25 tablets after 8 weeks to 12 weeks (interval 3; LTT study days 57 to 84), and 15 tablets after 12 weeks to 16 weeks (interval 4; LTT study days 85 to 112). Thus, this subject is considered to have taken ≥ 14 tablets per 4 weeks for 12 weeks (i.e., intervals 1, 3 and 4), ≥ 20 tablets per 4 weeks for 8 weeks (i.e., intervals 1 and 3), and ≥ 25 tablets per 4 weeks for 4 weeks (i.e., interval 3). See Section 5.5 for the definition of LTT study days.

eDiary exposure will also be summarized by subgroup level and overall for treated subjects for all subgroups of interest described in Section 4.2.6.

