## 6.5 Early Discontinuation from the Study

Subjects MUST discontinue investigational product (and non-investigational product at the discretion of the investigator) for any of the following reasons:

- Withdrawal of informed consent (subject's decision to withdraw for any reason)
- Any clinical adverse event (AE), laboratory abnormality or intercurrent illness which, in the opinion of the investigator, indicates that continued participation in the study is not in the best interest of the subject
- Pregnancy
- Termination of the study by Biohaven Pharmaceuticals
- Loss of ability to freely provide consent through imprisonment or involuntary incarceration for treatment of either a psychiatric or physical (e.g., infectious disease) illness
- No migraine treated with study medication prior to Week 8 visit of Long-Term Treatment Phase.
- Poor compliance with study procedures and visits, including poor completion compliance with evening reports in eDiary. Subjects with 6 or more missed evening reports per month, in 2 (sequential or non-sequential) months, should be discontinued from the study for poor compliance, after discussion with Sponsor.
- Please see section 6.2.5 for guidance on study discontinuation based on results from the S-STS.

All subjects who discontinue should comply with protocol specified End of Treatment procedures as outlined in Table 1 or Table 2. The only exception to this requirement is when a subject withdraws consent for all study procedures or loses the ability to consent freely (i.e., is imprisoned or involuntarily incarcerated for the treatment of either a psychiatric or physical illness

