Secondary safety endpoints as described in Section 4.6.2 will be assessed by several study drug exposure groups for treated subjects. The number and percentage of subjects with hepatic-related SAEs by SOC, PT and severity, hepatic-related AEs leading to study drug discontinuation by SOC and PT, and concurrent elevations of AST or $ALT > 3 \times ULN$ with $TBL > 2 \times ULN$ will be shown by subgroup level and overall for extrinsic exposure subgroups (see Section 4.6.2). Only treatment-emergent AEs and on-treatment laboratory test values will be included.

4.6.3.5 *Number and Severity of Migraine Days per Month*

Subjects are instructed to report migraine status (yes, no, unable to recall) and severity (mild, moderate, severe, unable to recall) in their diaries every day.

Migraine days per month will be assessed as “migraine days per 4 weeks” to correspond with the 4-week visit schedule. Analyses will be based on the OP and LTT analysis periods for evaluable treated subjects, i.e., treated subjects who had ≥ 14 days of data (not necessarily consecutive) in both the OP analysis period and at least one 4-week interval in the LTT analysis period.

- A day of data is defined as an eDiary record with complete date and {yes or no} response to having a migraine. If a subject has multiple responses or migraine severities on the same date, then the most severe migraine last sequenced chosen. Only days of data are included in analyses.
- A migraine day is defined as a day of data with a “yes” response to having a migraine.
- 4-week (28-day) intervals are defined from LTT start as: interval 1 (≤ 4 weeks; LTT study days 1 to 28), interval 2 (> 4 to ≤ 8 weeks; LTT study days 29 to 56), ..., interval 13 (> 48 to ≤ 52 weeks; LTT study days to 336 to 364), interval 14 (> 52 to ≤ 56 weeks; LTT study days to 365 to 392). See Section 5.5 for the definition of LTT study days.

Thus, the total numbers of days of data and migraine days are calculated for the OP analysis period and for each 4-week interval in the LTT analysis period.

OP records will come from the screening epoch, whereas LTT records will be come from the treatment epoch.

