5.2.3 Rimegepant Exposure

Rimegepant exposure subgroups are derived from parameters defined in Section 4.8.1 as follows:

- Time on rimegepant subgroups are based on quintiles of total weeks on treatment (< P20, ≥ P20 to < P40, ≥ P40 to < P60, ≥ P60 to < P80, ≥ P80) based on eDiary for treated subjects pooled across enrollment group. Percentiles will be rounded to 1 decimal place.
- Cumulative rimegepant exposure subgroups are based on quintiles of the total number of study drug tablets taken (< P20, ≥ P20 to < P40, ≥ P40 to < P60, ≥ P60 to < P80, ≥ P80) based on eDiary for treated subjects pooled across enrollment group. Percentiles will be rounded to integers.
- Average rimegepant exposure subgroups are based on average rimegepant exposure (tablets per 4 weeks), which is calculated as 4*cumulative rimegepant exposure/time in the LTT period for treated subjects pooled across enrollment group.

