5.3 Derived Dates

Derived dates for defining analysis periods are defined as follows:

- OP start date/time: Earliest complete date during the screening epoch in the eDiary.
- OP end date/time: Latest complete date during the screening epoch in the eDiary.
- LTT start date/time: Earliest complete date during the treatment epoch in the eDiary.
- LTT end date/time: Latest complete date during the treatment epoch in the eDiary.
- Study drug first dose date/time: Earliest complete date where subjects indicated that they took medication during the treatment epoch in the eDiary.
- Study drug end dose date/time: Latest complete date where subjects indicated that they took medication during the treatment epoch in the eDiary.
- Study drug last dose date/time: Study drug end dose date derived only for subjects who have non-missing completion status on the Study Exit Status CRF. Thus, in an interim analysis, all post-treatment data will be included for a subject who is still on study. At the last database lock, the last dose date will be equal to the end dose date for treated subjects.
- EOT visit date: Maximum of the following: (1) LTT end date/time; (2) latest complete visit date excluding folder name “follow-up safety visit” on the Visit Date CRF. This is derived only for subjects who have non-missing completion status on the Study Exit Status CRF.

- Last contact date: (1) Complete death date, if it exists; (2) otherwise, the maximum complete date of the following: AE start/stop; ECG; eDiary; enrollment; informed consent; laboratory collection; non-study medication start/stop; physical measurement; procedure; rating scale; questionnaire; screening; study completion/discontinuation; vital sign; visit.

No imputations are performed on these derived dates. Complete dates are those with valid, non-missing day, month, and year.

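### Unreported eDiary days count as zero tablets but stay in the denominator, so average exposure can err only downward, by an amount the documents do not allow us to size

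*SAP*

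**What the plan says.** **Exposure (SAP 4.8.1 and 5.3).**

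- For a day without study drug data, "then it is assumed that the subject did not take study drug that day".
- Cumulative exposure is "derived by summing number of tablets across records with complete dates for subjects who reported taking study medication during the treatment epoch in the eDiary".
- The per-4-week average is "derived as 4*cumulative rimegepant exposure/time in the LTT period".
- The LTT period is bounded by diary dates: "LTT start date/time: Earliest complete date during the treatment epoch in the eDiary" and "LTT end date/time: Latest complete date during the treatment epoch in the eDiary".

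**Subgroups.** SAP 4.2.6 cuts average exposure at 2, 8 and 14 tablets per 4 weeks, and cuts the EOD+PRN group at 14 alone. SAP 4.8.1 adds 12.6 and 11.2 as the 90% and 80% EOD compliance categories. In SAP 5.2.3 the cumulative-tablet and time-on-rimegepant quintiles are "based on eDiary for treated subjects pooled across enrollment group", and the average-exposure formula is repeated.

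**The same diary elsewhere.** For migraine days (SAP 4.6.3.5), "Only days of data are included in analyses". Counts are prorated to 28 days and at least 14 data days are required. SAP 4.2.8 states a general rule of observed data only.

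**Controls on missing entries.** Protocol 6.5: "Subjects with 6 or more missed evening reports per month, in 2 (sequential or non-sequential) months, should be discontinued". Protocol 7.4 sends missing dosing data to a Data Clarification Record or a Medication Reconciliation Form. SAP 4.8.1 mentions that form only as the site source in the eDiary compliance table. It also summarises drug-accountability exposure separately, and a listing flags subjects whose two cumulative totals differ by 10 tablets or more.

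**The concern.** The zero rule is a single-value imputation that works in one direction. A missing day inside the LTT span puts nothing in the numerator and one day in the denominator. It can lower recorded exposure and never raise it. The migraine-day analysis, which uses the same diary, removes such a day from both sides, and the SAP gives no reason for the difference.

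Exposure matters here because liver tests are the main adverse event of interest (Protocol 1.3.4), and the contribution of exposure to liver-test abnormalities is an exploratory objective (Protocol 2.2). SAP 4.2.6 lists average exposure as a key factor. It defines eDISH plots and liver-test elevation tables (SAP 4.6.3.1) and adverse event tables (SAP 4.8.2). A subject who takes tablets without recording them could be placed in too low an exposure category, along with any event that subject had. No subgroup is re-derived from another source, and no sensitivity analysis of the zero rule is planned.

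**Working it through.** **1. Reproduce the plan's figures.** Full EOD dosing is 28/2 = 14 tablets per 4 weeks. Then 0.9 × 14 = 12.6 and 0.8 × 14 = 11.2, as in SAP 4.8.1.

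**2. Steady under-reporting (assumed range).** The documents give no rate of missing diary days. Suppose m days in every 28 are unreported and unreconciled throughout LTT, lie inside the LTT span, and carry the subject's usual tablet rate. Recorded average = true average × (1 − m/28).

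| m per 28 days | Factor | True 14 recorded as | True average needed to record 14 |
|---|---|---|---|
| 1 | 0.964 | 13.5 | 14.5 |
| 3 | 0.893 | 12.5 | 15.7 |
| 5 | 0.821 | 11.5 | 17.0 |

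Taking a month as 28 days, m = 5 is the most that never meets the 6-report limit in Protocol 6.5.

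**3. Twelve weeks of perfect EOD dosing.** 42 tablets over 84 days gives 4 × 42/12 = 14.00, exactly on the <14/≥14 cut. The data-day version is 28 × tablets/data days.

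| Unrecorded dosing days | SAP average | Data-day average |
|---|---|---|
| 0 | 14.00 | 14.00 |
| 1 | 4 × 41/12 = 13.67 | 28 × 41/83 = 13.83 |
| 3 | 4 × 39/12 = 13.00 | 28 × 39/81 = 13.48 |
| 5 | 4 × 37/12 = 12.33 | 28 × 37/79 = 13.11 |
| 9 | 4 × 33/12 = 11.00 | 28 × 33/75 = 12.32 |

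Under the SAP formula, one lost tablet crosses the 14 cut, five cross 12.6 and nine cross 11.2. Nine is still below the 10-tablet listing flag. Over 52 weeks the same nine tablets lower the average by 9 × 28/364 = 0.69, against 9 × 28/84 = 3.0 over 12 weeks.

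**4. Where the rule does no harm.**

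- Nothing taken on the missing days: with 26 tablets in 364 days and 20 days missing, the SAP gives 28 × 26/364 = 2.00, which is right. Data-day proration gives 28 × 26/344 = 2.12, which is too high.
- Missing days at the end: LTT stops at the last diary date, so 37 tablets over a 74-day span still give 28 × 37/74 = 14.0.
- One missing non-dosing day under EOD: the SAP gives 14.00, and data days give 28 × 42/83 = 14.17.

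**5. Reach of the two mechanisms.**

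- Zero numerator with a full denominator: average-exposure categories, the EOD+PRN split and the 12.6/11.2 categories.
- Zero rule alone: cumulative-tablet quintiles, and the subgroups with ≥14 tablets for ≥12 weeks or ≥20 tablets for ≥4 weeks, which are raw tablet counts per 4-week interval.
- Not affected by interior gaps: time-on-rimegepant quintiles and patient-years, which depend on first and last dose dates. EOD+PRN subjects also enter the near-daily subgroup whatever their tablet count.

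**The case against.** The strongest case for the plan is that exposure should count documented tablets, and that a conservative count is defensible. About 1800 of the 2000 subjects (1200 + 600) dose as needed, so zero is a plausible value for many missing days. Protocol 7.4 says missing dosing data will be corrected, and staff compare the diary with returned drug at each visit. SAP 4.4.2 counts eDiary non-compliance as a significant deviation. Drug-accountability exposure is already summarised. Proration would credit tablets nobody recorded: 7 tablets on 14 data days would become 14 per 4 weeks, which enlarges the heavily exposed group with imputed use. Many subjects would not change category in any case: a PRN subject truly at 6 with five misses per 28 days becomes 6 × 23/28 = 4.9, still in the ≥2 to <8 band.

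Much of this stands. It rules out making proration the primary derivation, and it makes the bias conditional. It does not close the gap. SAP 4.8.1 does not say that reconciled doses enter eDiary exposure. The accountability summary does not feed any subgroup, and the 10-tablet flag marks a listing only. The average-exposure tables therefore cannot show whether they depend on the zero rule.

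A reader might also infer that three missed reports are enough to fail the 12.6 category. That needs three in every 28 days throughout LTT (12.5). Three in total over 12 weeks give 13.0 at worst.

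**Conclusion.** The point holds in a conditional form. The zero rule can only lower average exposure, and it does so when a tablet was taken on a day inside the LTT span that was neither recorded nor reconciled. Under the assumed 1 to 5 missed days per 28, sustained and carrying the usual tablet rate, the loss is 4% to 18%. The EOD+PRN split is the most fragile place, because perfect adherence sits on the cut and one unrecorded tablet crosses it.

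Two stronger readings are tempting and not supported. One is that every exposure subgroup is biased low: time-on-rimegepant quintiles are untouched by interior gaps, and the cumulative and interval-count subgroups have no inflated denominator. The other is that an exposure-response signal is diluted or that events move to low-exposure strata. This could happen, but the documents give neither a missing-day rate nor a recovery rate, so neither its occurrence nor its size can be shown. The exposure analyses are descriptive, and the matter is one of interpretation within them.

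The protocol text supplied does not contain the 12-week PRN cohort that the SAP attributes to protocol version 6, so the provisions of Protocol 6.5 and 7.4 are read from an earlier version.

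**What to change.** In SAP 4.8.1:

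1. State that doses recovered by Data Clarification Record or Medication Reconciliation Form count as eDiary exposure.
2. Keep the zero-tablet derivation, labelled as the documented lower bound.
3. As sensitivity analyses, repeat the average-exposure categories, and the key liver-test, eDISH and adverse event tables built on them, in two ways: (a) 28 × tablets/data days, with at least 14 data days, where a data day has a complete date and an answer to the drug-taken question; (b) drug-accountability tablets, using the average already defined in SAP 4.8.1.

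Both versions use data already collected, so the cost is SAP wording and a little more programming. Neither is a clean replacement. Version (a) overstates exposure if no tablets were taken on the missing days, and it does not settle the EOD+PRN cut: one lost dosing day still gives 13.83. Version (b) counts only kits with a recorded return, and treats every tablet not returned from them as taken. If the three versions agree, the zero rule is harmless; if they differ, the exposure tables need to be read with that in view.
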